# **1. Introduction**

Atrial fibrillation (AF) is the most prevalent type of arrhythmia within an adult population and is characterised by disorganised, chaotic, electrical activity and thus ineffective atrial contraction causing irregular ventricular contraction (Wyndham, 2000). AF can be categorised into three different groups: paroxysmal, persistent, and permanent. The prevalence of AF increases with age and is associated with, but not limited to, a range of risk factors including hypertension, obesity, and alcohol consumption (Staerk, *et al.*, 2017). There is a plethora of both cardiac and non-cardiac causes of AF and the cause is not always clear for each patient. Furthermore, causes of AF can also present as the by-product of AF, this increases the difficulty in determining the individual patient's cause of onset. A diagnosis of AF can be incidental as not all patients are symptomatic. If AF goes undetected, this puts the patient at an increased risk of blood clot formation and stroke (Markides and Schilling, 2003).

Patients suspected of having AF are routinely referred for a transthoracic echocardiogram (TTE). It is common for AF patients to have a dilated left atrium (LA) and this can be visually confirmed in addition to the LA area and volume measurements (Van De Vegte, et al., 2021). However, as LA measurements are limited to area and volume size, LA strain measurements may be taken but these are not routinely performed during standard TTEs. LA strain is measured using a type of speckle-tracking echocardiography (STE) technique which focuses on the subtle longitudinal changes within the myocardium to analyse myocardial deformation (Gan, et al., 2018). Strain imaging of the LA produces three functional strain values (contractile, conduit and reservoir) which correspond to different stages of the cardiac cycle (Jarasunas, et al., 2018). As patients in AF lack normal atrial contraction and have a loss of atrial kick, it is expected that the contractile strain, associated with LA contraction, is not present. However, the conduit and reservoir functions can still be compared across all three study groups to create a scale to suggest and predict whether a patient is likely to develop AF in the future; prior to any changes in LA size. Furthermore, this can then be further compared to determine whether there are any significant differences in strain patterns between the different groups of AF.

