# 1.1 Background

From the current literature available (*see document Literature Review Table*), it has been suggested that there is a correlation between AF and LA strain values. Existing literature suggests that patients in AF have a reduced LA strain value compared to patients in NSR. However, there are limited studies which also include controlled hypertensive patients despite collecting data regarding blood pressure. Furthermore, the majority of literature reviewed appears to focus on patients that have other comorbidities, and it could be argued that these can affect the parameters measured and analysed. This includes studies involving patients with valvular pathologies such as aortic stenosis and aortic valve replacements as well as studies involving patients with potential structural heart deformations such as those seen with heart failure or following a myocardial infarction. These factors may alter strain patterns and LA size as a result. By listing these factors as exclusion criteria, this study should minimise any external and uncontrollable factors which may affect LA strain value and LA size.

Furthermore, some studies do not have a standardised zero-reference point as some studies used the P wave for NSR and the R wave for AF patients which may cause a discrepancy in results. In this study, it has been agreed that the zero-reference point will be the R wave to create R-R cycles. This is because the P wave is not present in AF and thus cannot be used as a definitive reference point within the AF group. Both groups will have R waves present and therefore, the reference-point can be standardised across all three groups. Additionally, many of the studies reviewed appear to focus on only one LA strain and phase within the cardiac cycle. However, some do include all three. This study will include all three strain values as well as peak atrial longitudinal strain (PALS) values. However, statistical analysis may not be doable for the contractile phase as this is not present in patients with AF. The biggest pitfall that is common to most, if not all, studies reviewed is that the methods used to calculate LA strain were originally designed to measure global longitudinal strain (GLS) of the left ventricle (LV). This study utilises the automated function imaging (AFI) LA atrial strain tool provided by GE Healthcare which is specific to the LA as opposed to GLS methods to track the LV.

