#### 2.2.4 Eligibility Criteria

Patients must be in one of the following categories to be included: normal sinus rhythm, normal sinus rhythm with controlled hypertension and chronic atrial fibrillation (persistent or permanent). Patients with paroxysmal AF may also be included but only as part of subsequent analysis when comparing strain measurements between AF groups. Additionally, eligible patients must conform to the following inclusion and exclusion criteria.

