#### 2.2.5 Power Calculation

The study aims to investigate significant differences in atrial strain values between subjects with atrial fibrillation (AF), hypertension (no AF), and healthy volunteers. To

achieve statistical power for this study, a large enough sample size must be obtained. This will be achieved via the use of power calculations utilising G\*Power 3.1 Statistical support has been provided and a sample size calculation was based on data found within the literature and involved detecting the smaller difference of left atrium contractile % between subjects with atrial fibrillation and healthy volunteers. The following criteria will be utilised: alpha level of 0.05, beta level of 15% and statistical power of 85%. Hence using this minimum value to determine our sample size (expected difference of 4.0, power = 0.85 and SD  $\pm$  7.5) and one-way ANOVA at three levels, a minimum sample size of at least 78 subjects in each group will be required for this study, total of 234 participants required. See Appendix Figures 1 & 2 for power calculation plots.

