#### 2.2.6 Statistical Analysis Plan

Continuous data normality will be assessed utilising the Shapiro-Wilk test. Nonparametric data will be analysed via Mann-Whitney U tests and Kruskal-Wallis oneway ANOVA tests. If data shows a normal distribution, to compare the LA strain values between the control (NSR) and disease (AF) groups an independent T-test can be performed; this will establish whether there is an initial statistically significant difference between the two. Following this, to compare the mean strain values for each phase between the three groups, a one-way ANOVA must be performed. A one-way ANOVA can also be performed to determine any significant differences between the strain values between AF groups. These data analysis methods will also be repeated to analyse LA area and volume. To assess whether LA area and volume size correlate with LA strain, a Pearson correlation coefficient must also be performed. Furthermore, to determine whether LA strain may be used as an early predictor of AF, linear regression models must be adapted. For categorical data, such as gender, chisquared tests will be performed to determine any significant difference between groups. All statistical tests will be performed using the Prism GraphPad software.

It is expected that there will be a significant difference in strain values between NSR and AF participants. It is also expected that an increase in LA area and volume size will correlate with a decrease in LA strain values.

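### The NSR versus chronic-AF strain comparison largely confounds disease group with rhythm at the scan, so a significant difference is not evidence of early atrial change

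*Combined protocol and SAP*

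**What the plan says.** The hypotheses in section 2.1 set NSR against chronic AF, which section 2.2.4 defines as persistent or permanent. Section 2.2.6 gives the first test: "to compare the LA strain values between the control (NSR) and disease (AF) groups an independent T-test can be performed". A one-way ANOVA across the three groups follows for each strain phase. Under section 2.2, a significant result, above all between control and disease groups, opens the comparison among AF types.

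Sections 1 and 1.1 say that patients in AF lack atrial contraction, that contractile strain is therefore expected to be absent, and that this phase may not be analysable. Section 1 adds that "the conduit and reservoir functions can still be compared across all three study groups to create a scale to suggest and predict" future AF. Section 1.1 fixes the timing: "the zero-reference point will be the R wave to create R-R cycles". Section 2.2.5 nevertheless sizes the study on "detecting the smaller difference of left atrium contractile % between subjects with atrial fibrillation and healthy volunteers".

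Heart rhythm is among the data listed in section 2.2.2, but section 2.2.6 does not use it. Section 2.2.4 limits one AF group: "Patients with paroxysmal AF may also be included but only as part of subsequent analysis when comparing strain measurements between AF groups". There is one visit and no follow-up (sections 2.2.2 and 2.4). Sections 1.2 and 2.3 state the aim as early prediction of AF.

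**The concern.** By the protocol's own account, being in AF during the scan removes atrial contraction. Rhythm at the scan is then largely the same variable as disease group, and nothing in the analysis separates the two. A significant strain difference could mean that AF-prone atria deform abnormally, or only that an atrium in AF is not contracting. The early-predictor question needs the first meaning.

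AF patients scanned in sinus rhythm would share the controls' rhythm while having known AF. Paroxysmal AF is the likeliest source of such patients, and section 2.2.4 keeps that group away from controls.

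What is at stake is the reading of the result. Section 2.3 links it to closer monitoring and anticoagulation, and section 4.1 to monitoring and medication of participants.

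**Working it through.** **Inputs.** From section 2.2.5: "expected difference of 4.0, power = 0.85 and SD" 7.5, alpha 0.05, and "a minimum sample size of at least 78 subjects in each group will be required for this study, total of 234 participants required". The documents do not state whether the t-test is two-sided; two-sided is assumed.

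**1. The plan's own figure.** For group means 0, 2, 4, the effect size is f = √(8/3) / 7.5 = 0.2177, as on the G*Power printout in the Appendix. With N = 234, λ = f² × N = 11.093, the critical F on 2 and 231 df is 3.035, and power is 0.851. The sample size reproduces. (The figure captions give f = 0.25; that is a separate matter and is not used here.)

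**2. Illustration: the whole NSR–AF gap comes from rhythm.** Suppose the underlying atria are the same and AF lowers mean strain by k points only because contraction is absent at the scan.

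- Standard error of the difference: 7.5 × √(2/78) = 1.201.
- Smallest significant observed gap: 1.975 × 1.201 = 2.37 points.
- t-test: noncentral t with 154 df and noncentrality k / 1.201.
- ANOVA: means 0, 0, −k (hypertensive group equal to NSR), with λ = 78 × (2k²/3) / 7.5². At k = 4, λ = 14.79.

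| Assumed rhythm-only loss k | t-test significant | Three-group ANOVA significant |
|---|---|---|
| 2 | 38% | 38% |
| 3 | 70% | 73% |
| 4 | 91% | 94% |
| 6 | over 99% | over 99% |

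The value 4 is the plan's own contractile difference. If 20% of the AF group were in sinus rhythm at the scan, a 4-point loss would be significant about 75% of the time (simulation).

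**3. How far this reaches by phase.** For contractile strain, the mechanism is in the protocol's own words. For reservoir strain and PALS, it needs two assumptions that the protocol does not state: that reservoir equals conduit plus contractile when the R wave is zero, and that conduit strain is unchanged in AF. The SD of 7.5 is also carried over from contractile strain. Under these assumptions conduit strain is not affected.

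**4. Precision of a rhythm-matched contrast.** For n paroxysmal patients in sinus rhythm against 78 controls, the 95% CI half-width is t × 7.5 × √(1/n + 1/78). The values of n are assumed, because the plan sets none.

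- n = 30: 1.98 × 7.5 × 0.215 = 3.2 points
- n = 20: 1.98 × 7.5 × 0.251 = 3.7 points

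Power for a 4.0-point difference is 0.69 with 30 patients, 0.56 with 20 and 0.35 with 10.

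**The case against.** **The plan already deals with it.** Sections 1 and 1.1 disclose the missing contractile phase, conduit strain is tested separately, and a sinus-rhythm hypertensive group is in the design. This stands in part. But the study is still sized on contractile strain and section 2.2.6 still tests each phase. The hypertensive contrast is rhythm-matched, but that group does not represent AF.

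**Prediction is assigned to regression, not to the t-test.** True, but section 2.2.6 does not name the outcome of that regression. With one visit and no follow-up, the AF status available is that at the scan, so the same confounding applies.

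**The percentages restate the power calculation.** This stands. A reader might take 91% as a false-positive rate to set against 5%. It is not one: the null in section 2.1 is no strain difference between the groups, and in the illustration that null is false, so rejecting it is correct. The fault lies in the interpretation.

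**Stronger readings.** A reader might infer that the test will almost always be positive for rhythm reasons alone. The documents give no size for a rhythm effect on any phase, and the illustration gives only 38% at 2 points. Nor does section 2.2.5 say that the 4.0 reflects complete loss of contraction. A reader might also infer that only paroxysmal patients can be scanned in sinus rhythm. The protocol fixes no scan rhythm for any AF group.

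**The added contrast is weak.** This also stands. Paroxysmal patients may be included, but have no target number, and neither inclusion criterion 1 nor the screening categories in section 3.1 name them. Controls must be normotensive and otherwise healthy; that limit is not set for paroxysmal patients. They already have AF, and section 1 accepts that remodelling may be cause or consequence.

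**Conclusion.** The point holds as one of confounding and interpretation. The main comparison cannot separate an altered atrium from an atrium that was not contracting at the scan, and the plan records rhythm without using it. For contractile strain this rests on the protocol's own statements. For reservoir strain and PALS it is a possibility that depends on additive phases and an unchanged conduit part.

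The size is illustrative: 38%, 70% or 91% significance for assumed rhythm-only losses of 2, 3 or 4 points, at SD 7.5 and 78 per group. The documents do not show that a positive result would be due purely to rhythm. They do show that a positive result would not answer the early-predictor question.

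**What to change.** **Section 2.2.6.** Keep the NSR versus chronic-AF comparison. State that it shows a difference that includes the effect of rhythm at the scan, and that it is not evidence of early change. Using the recorded rhythm, add two exploratory contrasts among patients in sinus rhythm at the scan, each as a mean difference with 95% CI:

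- AF patients in sinus rhythm (mainly paroxysmal) versus NSR controls
- Hypertensive patients versus NSR controls

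**Section 2.2.4.** Widen the *only* wording so that paroxysmal AF may also enter the first contrast.

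**Cost.** Wording in two sections and two contrasts on variables the study already plans to record, with no new procedure. The downsides should be stated in the plan:

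- The number of paroxysmal patients is not set, so the first estimate may be imprecise (half-width about 3.2 points with 30 patients, 3.7 with 20).
- These patients already have AF and may have comorbidities that controls lack. The contrast removes the rhythm difference but does not by itself establish prediction, which a single visit without follow-up cannot show.
- The main NSR versus AF result becomes a more modest claim.

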#### 2.2 Method

Patient selection:

Potential candidates for this study will have been referred for a TTE by a healthcare professional. The referrals will be reviewed and if the patient meets the initial eligibility criteria, they will be considered as part of this study. The initial eligibility criteria consist of being over the age of 50 (although patients will be age-matched across the three groups) and falling within the control (normal sinus rhythm), disease-control (controlled hypertension) or disease groups (chronic AF).

Data collection:

The images obtained from the TTE scan will be stored on the ultrasound machine as well as the picture archiving systems (PACS) on the computer. The measurements to be compared are:

- Left atrium area
- Left atrium volume
- Left atrium strain measurement and analysis using the R wave

The first two measurements are routinely performed during TTEs, but atrial strain measurements are not routinely performed. This additional measurement will not affect or delay the TTE results and report from being sent back to the referrer or delay any further correspondences with other healthcare professionals. Atrial strain measurements will be conducted using the AFI LA atrial strain tool provided by GE Healthcare. These three measurements will be compared across the three groups and tested for a statistically significant difference. Providing that there is a significant

difference, particularly between the control and disease groups, a subsequent comparison will be conducted between the three groups of AF using the existing data.

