#### 2.2.2 Study Overview

- Study design quantitative, observational, case-control study.
- Patients will be assigned to one of three groups: control group (normal sinus rhythm), disease-control group (controlled hypertension) and disease group (chronic atrial fibrillation).
- Patients will be required to visit the department on one occasion. This will be as part of either a routine or urgent referral for a transthoracic echocardiogram (TTE).
- TTEs are stored on both the ultrasound machines and computer picture archiving systems (PACS). Measurements can be taken on either the ultrasound machine or on the PACS following the patient's scan. The data obtained from these scans that will be utilised include patient demographics, heart rate and rhythm, LA area and volume measurements as well as LA strain measurements. This will be pseudo-anonymised using two Excel spreadsheets and the document will be password encrypted on a NHS OneDrive account
- Study site: within the Cardio-Respiratory department at Withybush General Hospital, there are five sonographers. This creates a throughput of approximately 60 TTE scans per week. With an expected data collection period of five months, this would equate to approximately 1200 outpatient scans factoring in annual leave and sickness. Additionally, inpatient scans can boost this number, but is dependent on current demand.

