#### Inclusion criteria:

- Criterion 1: subjects will be included in the study if they are within one of the following groups:
  - Known to be in normal sinus rhythm, are normotensive and have no underlying health problems.
  - Known to be in normal sinus rhythm and have controlled hypertension. This must have been diagnosed by a healthcare professional and the patient should be taking appropriate antihypertensive medication.
  - Known to have chronic atrial fibrillation (persistent or permanent AF). This must have been diagnosed by a healthcare professional and the patient should be appropriately anticoagulated.
- Criterion 2: subjects should ideally be ≥ 50 years, but subjects will be age matched across all three groups.
- Criterion 3: patients should have an EF  $\ge$  50%.
- Criterion 4: good quality TTE images.
- Criterion 5: No valvular pathologies.
  - Patients with AF that have < moderate valvular pathologies may be considered (as per the British Society of Echocardiography Guidelines).

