# 4.4 Confidentiality

For patients that wish to participate in this study, all signed Informed Consent Forms will be securely stored in the Investigator Site File within the Cardio-Respiratory Department and must not leave the department under any circumstances. The participant data will undergo pseudo-anonymisation via the use of two password-protected excel spreadsheets. One spreadsheet will contain participant numbers and corresponding hospital ID numbers. The second spreadsheet will include participant numbers along with patient demographics (i.e., sex, age, participant group, reason for patient referral, etc.). This data will be encrypted and the folder it resides in will also be encrypted and password protected. This will be stored on an NHS OneDrive account on a departmental computer. General data protection regulation (GDPR) will be maintained and followed throughout.

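### LA area and volume carry no body-size index and are compared unadjusted, so group differences in body size or sex can mimic or mask remodelling

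*Combined protocol and SAP*

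**What the plan says.** Section 2.2 (Method) lists the measurements to be compared, including LA area and "Left atrium volume", with no index attached. Section 2.2.6 first sets out the strain tests: t-test and one-way ANOVA, or their rank-based counterparts. It then adds "These data analysis methods will also be repeated to analyse LA area and volume". LA size is used a second time: "To assess whether LA area and volume size correlate with LA strain, a Pearson correlation coefficient must also be performed".

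On the data available, section 2.2.2 lists "patient demographics, heart rate and rhythm, LA area and volume measurements as well as LA strain measurements", and section 4.4 lists "patient demographics (i.e., sex, age, participant group, reason for patient referral, etc". Neither names height, weight, BMI or body surface area, and no other section does.

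On comparability, the inclusion criteria in section 2.2.4 say "subjects will be age matched across all three groups". No other matching factor is given. For sex the plan offers only this: "For categorical data, such as gender, chisquared tests will be performed to determine any significant difference between groups". Nothing follows from the result. The linear regression in section 2.2.6 concerns strain as a predictor of AF. It names no covariates and does not address LA size.

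**The concern.** Larger people have larger atria without disease, so LA area and volume carry body size as well as remodelling. The documents give reasons to expect the groups to differ. The Introduction ties AF to "a range of risk factors including hypertension, obesity, and alcohol consumption". Controls must be normotensive and free of other health problems, a restriction that the AF and hypertensive groups do not share. No exclusion criterion limits body size.

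LA size is not incidental. The research question (1.2) and both hypotheses (2.1) link strain to LA area and volume. The rationale in sections 1 and 2.3 is that strain may change before the atrium dilates. That argument needs a measure of dilation that is not partly a measure of the person. Strain is a percentage, whereas area and volume are not scaled to the participant. An imbalance in body size or sex could therefore distort the size of the LA difference between groups, and through it the correlation pooled over groups.

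**Working it through.** **The plan's own figure.** The only sample-size figure is for contractile strain. Section 2.2.5 gives a difference of 4.0, SD 7.5, alpha 0.05 and power 0.85. With group means at 0, d/2 and d:

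- f = (4.0/7.5) × √(1/6) = 0.21773, matching the G*Power output in the Appendix.
- λ = f² × 234 = 11.093; critical F(2, 231) = 3.0349; power = 0.8509.

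The total of 234 (78 per group) is reproduced. It does not involve LA size, so nothing below changes it.

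**Inputs for the illustration.** The documents give no mean or SD for LA volume and no body-size figures. Assumed: mean 60 mL; CV 25%, 30% or 35% (SD 15, 18 or 21 mL); volume proportional to body surface area (BSA); equal indexed volume in the two groups. From the documents: 78 per group and a two-sided 5% test.

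**Shift in the mean.** Shift = BSA gap × 60 mL, so 3% gives 1.8 mL, 5% gives 3 mL and 10% gives 6 mL.

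**Hand check at CV 30%.** SE = 18 × √(2/78) = 2.88 mL. The rejection rate is P(|Z + shift/SE| > 1.96).

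- 3 mL: 3/2.88 = 1.04, rate about 0.18.
- 6 mL: 6/2.88 = 2.08, rate about 0.55.

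**Noncentral t (154 df) over the CV range.** Standardised shift = BSA gap / CV; noncentrality = standardised shift × √(78/2).

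| BSA gap | CV 25% | CV 30% | CV 35% |
|---|---|---|---|
| 3% | 0.116 | 0.095 | 0.083 |
| 5% | 0.237 | 0.179 | 0.144 |
| 10% | 0.699 | 0.543 | 0.426 |

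Dividing by BSA returns each rate to about 0.05 under the same proportionality assumption.

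**Sex.** Standardised shift = (sex effect in SD) × (difference in male share). For an assumed effect of 0.3 to 0.8 SD, a 20-point difference in male share gives rejection rates of 0.066 to 0.168. A 30-point difference gives 0.086 to 0.319.

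**Correlation with strain.** Two effects must be kept apart. Within a group, body-size variation unrelated to strain adds noise to LA size and pulls the correlation towards zero. Across pooled groups, a body-size gap that lines up with the strain gap adds to the correlation. If AF patients are larger, that is the direction the plan expects; if they are smaller, it works against it. No figure is given here, because the documents supply nothing to base one on.

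**The case against.** The strongest case on the other side has five parts.

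- **Silence is not a choice.** No section says that LA size will be left unindexed, and the list in section 4.4 is open-ended. This stands as to wording: use of absolute values is inferred. But a plan followed as written would analyse unindexed area and volume, and nothing commits the study to recording what an index needs.
- **The imbalance is not shown.** A reader might infer that false LA enlargement is bound to appear. The documents do not support that. They give no body-size figures, all participants are patients referred for echocardiography (2.2.3), and an imbalance could mask enlargement as easily as mimic it. An imbalance is plausible, not certain.
- **The no-remodelling null is unrealistic.** Section 1 already treats a dilated atrium in AF as established. This stands: the rejection rates only show how sensitive the test is. The practical harm is a biased size of difference, 3 or 6 mL on the assumed values.
- **LA size is secondary.** A reader might infer that the main result is undermined. It is not: the key outcome in section 2.3 is the strain difference, and the sample size was set on strain. Section 2.1 states no separate hypothesis of a group difference in LA size. LA size enters the hypotheses through its link with strain.
- **Indexing has its own bias.** Dividing by BSA can under-call enlargement in very obese participants, and obesity is the imbalance feared here. This is a reason to report both forms, not to leave body size unaddressed.

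**Conclusion.** The concern holds as a gap in the control of confounding for the LA size analyses. Area and volume are named without an index, tested without adjustment in groups matched on age only, and correlated with strain in that form. If body size or sex differs between groups, part of an LA size difference, and of the pooled correlation, can be body size or sex and not remodelling. The bias may run in either direction, and within groups the main effect on the correlation is noise.

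On assumed values only, a 5% BSA gap gives a 3 mL shift and a rejection rate of about 14-24%. A 10% gap gives 6 mL and about 43-70%. These figures rest on strict proportionality of volume to BSA and on a CV of 25-35%, neither of which is in the documents. They are for volume; no figure is given for area. The strain group comparison and the total of 234 stand. The change should be made, but it does not threaten the main comparison.

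**What to change.** 1. **Sections 2.2.2 and 4.4:** add height and weight to the data recorded at the scan visit. Where consent follows the scan, take them from the existing record.
2. **Sections 2.2 and 2.2.6:** make LA area and LA volume divided by BSA the variables for the group comparisons and for the correlation with strain.
3. **Section 2.2.6:** include sex as a covariate for all participants in the LA size comparison, since indexing may not remove all of a sex difference. This means a linear model with group and sex, because the listed t-test, one-way ANOVA and rank tests carry no covariate.
4. **Reporting:** give absolute area and volume alongside, because of the under-calling in very obese participants.
5. **Missing height or weight:** such participants appear only in the absolute-value analysis. Indexed and unindexed values (mL/m² and mL for volume) are not mixed in one comparison.

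The cost is two recorded values, a BSA calculation and one division per LA measure for each participant, plus one modest change of model. The scan, the strain analyses and the sample size do not change. The real difficulty is timing. Consent may be given by telephone after the scan (2.2.3, 3.2), and the extra measurements are made once the patient has left (4.10), so some heights and weights will depend on existing records. The documents do not say how complete those are, so the requirement should be written in before recruitment starts.

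### No primary outcome, primary test or multiplicity rule is named, so the 0.05 set for one ANOVA is not carried to the study's conclusion

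*Combined protocol and SAP*

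**What the plan says.** Section 1.1 sets the scope of the strain outcomes: "This study will include all three strain values as well as peak atrial longitudinal strain (PALS) values". It also warns that "statistical analysis may not be doable for the contractile phase as this is not present in patients with AF". So there are four strain outcomes, or three if the contractile phase drops out.

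Section 2.2.6 first offers an independent t-test between NSR and AF, worded as something that can be done, and says "this will establish whether there is an initial statistically significant difference between the two". A one-way ANOVA across the three groups must then follow for each phase, whatever the t-test shows. Mann-Whitney and Kruskal-Wallis tests replace these if the data are not normal. Then: "These data analysis methods will also be repeated to analyse LA area and volume".

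The only error rate is in section 2.2.5, as part of the sample size: "alpha level of 0.05, beta level of 15% and statistical power of 85" per cent. That calculation "involved detecting the smaller difference of left atrium contractile % between subjects with atrial fibrillation and healthy volunteers".

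Section 2.1 states a null and an alternative hypothesis about atrial strain in general. Section 2.3 speaks of key outcomes in the plural. Neither says which strain value, or which test, decides the hypothesis.

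**The concern.** The hypothesis in section 2.1 is generic. A significant result on any one strain value, by either test, could be reported as rejecting it, and each further opportunity raises the chance of a false positive above 0.05. The t-test and the ANOVA can also fall on opposite sides of 0.05 for the same outcome, and no rule says which one answers the NSR-AF question.

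The sample size does not supply a primary outcome by default. It rests on contractile strain, the one measure that section 1.1 doubts can be analysed in AF.

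The documents do not present the study as exploratory. They state hypotheses, alpha and power, and sections 1.1 and 2.3 link the findings to monitoring and anticoagulant use.

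**Working it through.** **1. Reproduce the plan's figure.** Inputs from section 2.2.5: "expected difference of 4.0, power = 0.85 and SD" of 7.5, alpha 0.05, three groups. Group means of 0, 2 and 4 have a between-group SD of √((4+0+4)/3) = 1.633, so f = 1.633/7.5 = 0.2177, the G*Power input in Appendix Figure 1. With N = 234, λ = f²N = 11.093, critical F(2, 231) = 3.035 and power = 0.851. All match the printed output. The plan's result is "a minimum sample size of at least 78 subjects in each group will be required for this study, total of 234 participants required". For one three-group ANOVA on one outcome, 0.05 is therefore right.

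**2. Count the outcomes.** Strain: contractile, conduit, reservoir and PALS, so four, or three without contractile. LA area and volume bring the total to six, or five.

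**3. One outcome, two tests.** Under no true difference, with 78 per group and two-sided tests (sidedness is not stated), simulation gives 5.0% for the t-test, 5.0% for the ANOVA and 2.5% for both. Either test: 5.0 + 5.0 − 2.5 = 7.5%.

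**4. Several outcomes, either test.** For k independent outcomes the rate is 1 − (1 − 0.0752)^k. Correlated outcomes were simulated as equicorrelated normal variables. The documents give no correlation, so 0 to 0.9 is assumed.

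| Outcomes | Correlation 0 | 0.7 | 0.9 |
|---|---|---|---|
| 3 strain values | 21% | 16% | 12–13% |
| 4 strain values | 27% | 20% | 14% |
| 3 strain + area + volume | 32% | 22% | 15% |
| 4 strain + area + volume | 37% | 24% | 16% |

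**5. One test per outcome.** If the optional t-test is skipped and only the ANOVA is run, independent outcomes give 1 − 0.95^k: 14.3% for three, 18.5% for four, 22.6% for five and 26.5% for six. For three strain values tested only by the NSR-AF t-test, the rate is about 8% at correlation 0.9.

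**6. Disagreement between the tests.** With the planned means 0, 2, 4 and SD 7.5, the t-test and ANOVA give different answers at 0.05 in about 7% of simulated studies.

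**7. Power of a single NSR-AF contrast.** The noncentrality is 4/(7.5 × √(2/78)) = 3.33. At two-sided 0.05 with 78 per group, power is about 91%, provided the 4.0 and 7.5 apply to the measure chosen.

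**8. Cost of adjusting every outcome instead.** Bonferroni over six ANOVAs (0.05/6 = 0.0083) cuts power at N = 234 to 64%, and 342 participants would be needed for 85%. Over five (0.01) the figures are 66% and 330.

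**The case against.** Four points on the other side are sound and limit the claim.

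- A reader might infer that the study's alpha is really 24–37%. The documents do not support that. The range is for six outcomes, two tests each, and assumed correlations of 0.7 down to 0. It includes LA area and volume, whose group differences do not decide the section 2.1 null, which concerns NSR-AF strain and the strain-size correlation. It also counts contractile strain, which may not be analysed. An ANOVA for PALS is itself inferred, since section 2.2.6 requires one for each phase and section 1.1 lists PALS apart from the phases.
- All the rates suppose no true difference on any outcome. The protocol expects the opposite: the Introduction anticipates that contractile strain is absent in AF and cites literature showing lower strain in AF.
- The t-test is optional in wording and is introduced as the test of NSR against AF. The ANOVA brings in the hypertensive group and asks a broader question, so differing results are not always a contradiction. What is missing is a statement of which one decides.
- A reader might infer that any significant test unlocks the AF-subtype comparison. The Study Summary ties it to a difference between NSR and AF patients, and section 2.2 points particularly to control against disease. The wording is loose, because no outcome or test is named, but it does not say any test.

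None of this supplies a primary outcome, a primary test or a multiplicity rule.

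**Conclusion.** The concern holds as an omission, not as a wrong figure. The 0.05 in section 2.2.5 is correct for the ANOVA it was set for, and 234 reproduces exactly, but nothing carries that level to the conclusion on atrial strain.

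If no true differences exist and both tests are run, the chance of at least one significant result is about 7.5% for one outcome, about 12–27% for the three or four strain values, and about 15–37% with LA area and volume. The strain range is the one relevant to the section 2.1 hypothesis on strain. The ranges rest on 78 per group, normal data, two-sided tests and an assumed common correlation of 0.9 down to 0. They leave out the AF-subtype ANOVA, the correlations and the regressions, so 37% is not a ceiling for the whole plan. They would be lower if only one test per outcome were run.

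This should be settled before the data are analysed.

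**What to change.** In section 2.2.6:

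- Name one primary strain measure that can be analysed in AF. The Introduction says reservoir and conduit function can both be compared across the three groups. Reservoir is a reasonable choice, but the choice belongs to the investigators.
- Make the NSR-AF contrast from one three-group model, at two-sided 0.05, the single primary test. It replaces the separate t-test.
- Report the other strain values, LA area and LA volume as secondary, either with Holm-adjusted p-values or labelled exploratory.
- State that the AF-subtype comparison depends on that primary test. This sharpens the looser wording in the Study Summary and sections 2.1 and 2.2.

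The cost is more than a sentence. Secondary outcomes carry less confirmatory weight; under Holm with five of them, the smallest p-value must fall below 0.05/5 = 0.01. Section 2.2.5 must restate its power for the chosen measure. It would be tempting to say that no power is lost, but this cannot be checked: the 4.0 and 7.5 were taken for contractile strain, and the documents give no such figures for reservoir or conduit. Only if they also apply to the chosen measure does N = 234 give about 91% power for the contrast.
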